
4 STUDY SCHEMA AND SCHEDULE OF ASSESSMENTS

The study schema is shown in [Figure 1](#) and the schedule of assessments is provided in [Table 1](#).

Figure 1: Study Schema

* If CDX-3379 is discontinued, the patient is considered to be discontinued from the study treatment.

Table 1: Schedule of Assessments

	Screening	Treatment Period			End of Treatment ³	Follow-up Period ⁴	
		Cycle 1		Cycle 2 and subsequent cycles		Day 1	30-day
		Day 1	Day 8	Day 15			
Visit Window ¹	Day -28 to -1		(+/- 1 day)	(+/- 1 day)			(+/- 3 days)
Informed consent ²	X						
Demographics and Medical history ⁵	X	X					
Tumor tissue	X ⁶						
Pregnancy test ⁷	X	X					
Vital signs ⁸	X	X	X	X	X	X	X
Physical examination ⁹	X	X	X	X	X	X	X
ECOG Performance Status (Appendix 3)	X	X			X	X	
12-Lead Electrocardiogram ¹⁰		X	X			X	
Serum chemistry ¹¹	X	X ¹²	X	X	X	X	X
Hematology ¹¹	X	X ¹²	X	X	X	X	X
Urinalysis ¹¹	X	X ¹²			X	X	
CDX-3379 PK sample ¹³		X ^{14,15}	X ¹⁴	X ¹⁴	X ^{14,15}		X ¹⁶
Biomarker blood sample ¹³	X	X ¹⁵	X	X	X ^{15,17}		X ¹⁶
Immunogenicity blood sample ¹³		X ¹⁵			X ¹⁵		X
Diagnostic Imaging / Response Assessment ¹⁸	X				X ¹⁸	X ¹⁸	X ¹⁸
Administer CDX-3379 ¹⁹		X			X		
Administer Cetuximab ²⁰					→		
Concomitant medication review ²¹	X	X	X	X	X	X	X
Adverse event monitoring ²²		X	X	X	X	X	X
Survival follow-up							X

Footnotes on next page

Footnotes for Table 1:

1. A delay in study treatment or performance of study visits due to holidays, weekends, inclement weather, or other unforeseen circumstances will be permitted and not considered a protocol deviation. However, significant delays (i.e., greater than one week) due to these reasons should be discussed with the Celldex Medical Monitor to reach consensus on subsequent scheduling. See Section 8.2 and Section 8.3 for management of dosing delays due to toxicity.
2. No study-specific procedures will be performed prior to receipt of signed Informed Consent (and, if applicable, Health Insurance Portability and Accountability Act [HIPAA] authorization). However, assessments performed according to standard of care prior to receipt of Informed Consent may be utilized to fulfill the screening requirement, if completed within the required window for screening.

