3. The End-of-Treatment (EOT) visit should be performed as soon as feasible following the decision to discontinue study drug dosing and prior to initiation of alternate therapies. This visit may be combined with the 30-day post-treatment follow-up visit, if the windows overlap, with required assessments completed once for the combined visit.
4. Follow-up visit should occur 30 (± 3) days after the last dose of CDX-3379. Thereafter, patients should be contacted (may be via telephone) every 12 (± 2) weeks until study closure for survival status and subsequent therapies. For patients who have discontinued study therapy for reasons other than progression, imaging studies to assess response should be obtained every 12 (± 2) weeks (relative to last disease assessment) until disease progression or until patients are started on subsequent therapy, whichever occurs sooner. For these patients, the first survival status may be scheduled to coincide with the first post-treatment disease assessment, rather than relative to the 30-day follow-up.
5. Medical history includes prior/concurrent conditions and cancer history including cancer mutation status and HPV status, prior treatments and surgical history. At Day 1, medical history is updated prior to administration of study drug.
6. Unless prior agreement is reached with the Medical Monitor for submission of archival tumor, biopsy is to be performed of an accessible site (primary or metastatic) that can be biopsied with acceptable clinical risk (as judged by the investigator), obtaining a minimum of 3-5 core biopsies for biomarker analysis. FNAs are not acceptable. The biopsy site chosen should not have been previously irradiated and must be distinct from RECIST 1.1 target lesions, unless the biopsy is obtained prior to the screening disease assessment.
7. Pregnancy tests are required only for women of childbearing potential (excluding patients who are post-menopausal with absence of menses for at least 1 year and/or surgically sterilized). A serum pregnancy test must be performed during Screening. If the serum pregnancy test is performed more than 7 days prior to Day 1, then a urine or serum pregnancy test must also be performed on Day 1 with results reviewed prior to dosing.

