7.2.2 Patient Eligibility

7.2.2.1 Inclusion Criteria

Patients may be included in the study only if they meet all of the following inclusion criteria prior to receiving study treatment:

1. Read, understood, and provided written informed consent, and if applicable, Health Insurance Portability and Accountability Act (HIPAA) authorization, after the nature of the study has been fully explained, and must be willing to comply with all study requirements and procedures.
2. Male or female patients who are 18 years of age or older.
3. Histologically or cytologically confirmed HNSCC that is recurrent or metastatic, not curable with local treatment modalities (e.g., surgery, radiation), and progressive (based on radiographic, clinical or pathologic assessment) during or subsequent to last therapy.
4. Human papilloma virus (HPV) negative tumor, as established by the local site. Acceptable standards include p16 immunohistochemistry (where a tumor is classified as p16-positive when showing diffuse nuclear and cytoplasmic staining in at least 70% of tumor cells) and/or assessment of HPV deoxyribonucleic acid (DNA).
5. Prior treatment must include (in any combination or sequence):
 - a. check-point inhibitor targeting programmed death receptor-1 axis (PD-1/PDL-1), unless not a candidate
 - b. cetuximab, with tumor progression during or within 6 months after completing treatment (regardless of any intervening therapies)
6. Measurable (target) disease by RECIST 1.1 criteria ([Eisenhauer, et al. 2009](#)) ([Appendix 2](#)). Target lesions selected for tumor measurements should be those where additional (e.g., palliative) treatments are not indicated or anticipated.
7. Willingness to consent for tumor biopsy from an accessible site (primary or metastatic) prior to initiating study therapy. In cases where a fresh biopsy is not feasible (i.e., if an accessible site cannot be biopsied with acceptable clinical risk or upon patient refusal), archival tissue may be submitted instead, after discussion with and approval by the medical monitor.
8. All residual toxicity related to prior radiotherapy or anticancer therapies (excluding alopecia, grade 2 fatigue, vitiligo or endocrinopathies on stable replacement therapy) must resolve to grade 1 severity or less (or returned to baseline) prior to receipt of study treatment.
9. Adequate electrolytes, liver, renal, and hematology function as defined below:
 - a. Hemoglobin \geq 9 g/dL
 - b. Absolute neutrophil count \geq 1500/mm³

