10.1.1 Screening Phase

Prior to the performance of any study-specific procedures, the patient will have the nature of the study explained to him/her, and will be asked to give written informed consent and if applicable, HIPAA authorization. Informed consent/HIPAA authorization must be obtained prior to any study-specific procedures that do not form a part of the patient's normal care. However, assessments performed according to standard of care prior to receipt of informed consent may be utilized to fulfill the screening requirement, if completed within the required window for screening.

The assessments outlined in for the Screening Visit in the Schedule of Assessments ([Table 1](#)) will be completed for each patient prior to inclusion in the study. The screening evaluations may be carried out over more than one visit.

Patients who are screened but do not meet all entry criteria (i.e., screen failures) will not be entered in the clinical database. Instead, a log of patients screened for the study, including the reason for study ineligibility, will be maintained at the study center. Once assigned, patient numbers for any screening failures, non-treated, unevaluable, or discontinued patients will not be re-used.

Study enrollment will occur only after confirming all inclusion criteria and none of the exclusion criteria have been met, and in accordance with instructions provided by Celldex.

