10.2.5 Safety Variables

10.2.5.1 Adverse Events

An AE is any untoward medical occurrence in a patient administered a study treatment. An AE can therefore be any unfavorable and unintended sign (including an abnormal laboratory finding), symptom, or disease temporally associated with the use of a study treatment, whether or not related to the study treatment. All observed or volunteered AEs regardless of suspected causal relationship to the study treatment will be reported as described in the following sections. For the purposes of this current study, CDX-3379 and cetuximab are considered “study treatment”.

For all AEs, the investigator is responsible for obtaining information adequate to determine the:

- Appropriate descriptive term: Adverse events should be reported using concise medical terminology, preferably referring to the syndrome/diagnosis rather than symptoms, when possible.
- Severity of the event: adverse event severity will be primarily assessed using National Cancer Institute Common Terminology Criteria for Adverse Events (NCI CTCAE), Version 5.0, division of Cancer Treatment and Diagnosis (DCTD), NCI, National Institute of Health (NIH), Department of Health and Human Services (DHHS) published November 17, 2017 at

https://ctep.cancer.gov/protocoldevelopment/electronic_applications/docs/CTCAE_v5_Quick_Reference_8.5x11.pdf

- Onset/resolution dates and outcome
- Causality: the relationship of each AE to study drug will be defined as “unrelated” or “related” to study treatment:
 - Unrelated: There is little or no possibility that the study drug caused the reported AE; and other factor(s) including concurrent illnesses, progression and expression of the disease state, concurrent medications, or a reaction to concurrent medications appear to explain the AE.
 - Related: there exists at least a reasonable possibility that the study treatments caused or contributed to the AE; an inability to identify an alternate etiology for an AE should not, by itself, justify a “related” attribution.
- Whether it meets the criteria for classification as an SAE (see Section 10.2.5.2)

The following study-specific points of clarification should be noted when considering AE reporting and recording:

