10.2.5.3 Adverse Event/Serious Adverse Event Reporting

The investigator is to report all directly observed AEs and all AEs spontaneously reported by the study patient. In addition, each study patient will be questioned about AEs.

Adverse events and SAEs should be recorded on the CRF from the time the patient has received at least one dose of study treatment through (whichever occurs first) either a) the 30-day post-treatment follow-up visit, or b) initiation of alternate anticancer therapy.

However;

- Any SAE occurring any time after the reporting period must be promptly reported if a causal relationship to study treatment is suspected.
- For AEs or SAEs with a causal relationship to the investigational product, follow-up by the investigator is required until the event or its sequelae resolve to \leq grade 1, or stabilize for at least three months after the last administration of study treatment (whichever is sooner).

All AEs will be reported on the AE page(s) of the CRF, while SAEs will also be reported in an expedited fashion using the SAE report. The AE CRFs and SAE reports must be completed in a consistent manner; for example, the same AE term, causality, severity, and onset/resolution dates should be used on both forms.

In case of an SAE (regardless of causality), an SAE report must be completed and submitted to Celldex within 24 hours of the site's notification of the event, irrespective of the extent of available AE information. This timeframe also applies to additional new information (follow-up) on previously forwarded SAE reports. The investigator is obligated to pursue additional information required for thorough evaluation of each SAE as may be requested by Celldex.

Serious adverse event reporting to regulatory authorities and all participating investigators will be conducted by Celldex in accordance with 21 Code of Federal Regulations (CFR) 312.32 and international regulations, as appropriate.

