7.2. Adverse events

Adverse events will be coded by MedDRA and summarized by system organ class (SOC), high level term (HLT), and preferred term (PT), and worst National Cancer Institute Common Terminology Criteria for Adverse Events (NCI CTCAE version 5.0) grade per patient. If a

patient reports more than one AE that was coded to the same SOC, HLT, or PT, the patient will be counted only once for that specific SOC, HLT, or PT.

Investigators will assess the relationship of each adverse event to each study drug. The relationship of each adverse event to study drug will be categorized as unrelated or related. If attribution is missing, the event will be assumed to be related to study drug.

All AE tables and listings will summarize treatment-emergent adverse events (TEAEs) defined as adverse events with onset on or after the date or the first dose of study drug or onset prior to the first dose of study drug but with worsened severity post-treatment. AEs without a severity rating that are reported post-treatment will be considered treatment-emergent. Presentations will include all adverse events through the 30 days following the last dose date.

The following TEAEs will be presented by severity:

- Serious adverse events
- All adverse events
- Adverse events related to CDX-3379
- Adverse events related to cetuximab, and
- Adverse events leading to study discontinuation.

All adverse events will be listed with MedDRA coding, onset and resolution dates, duration, seriousness, severity, relationship, actions, and outcome.

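### AE and SAE recording opens at first dose, after the screening core biopsy, so biopsy complications before dosing have no visible AE/SAE reporting rule

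*Protocol*

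**What the plan says.** **When recording starts.** Protocol Section 10.2.5.3: "Adverse events and SAEs should be recorded on the CRF from the time the patient has received at least one dose of study treatment". The definition in Section 10.2.5.1 has the same limit: "An AE is any untoward medical occurrence in a patient administered a study treatment". In Protocol Table 1 the row "Adverse event monitoring ²²" has no mark under Screening and begins at Cycle 1 Day 1. SAP Exhibit 4 shows the same.

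**What happens before that.** Screening runs from Day -28 to Day -1. Under Table 1, note 6, "biopsy is to be performed of an accessible site (primary or metastatic) that can be biopsied with acceptable clinical risk", "obtaining a minimum of 3-5 core biopsies for biomarker analysis"; fine needle aspirates are not accepted. The exception is in Section 7.2.2.1: where a fresh biopsy is not feasible, "archival tissue may be submitted instead, after discussion with and approval by the medical monitor".

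**Screen failures.** Section 10.1.1 says that patients who are screened but found ineligible "will not be entered in the clinical database". The site keeps a log with the reason for ineligibility.

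**How the SAP counts events.** SAP Section 7.2 treats as treatment-emergent an event starting on or after the date of first dose, and also one with "onset prior to the first dose of study drug but with worsened severity post-treatment". The SAP's Definitions table counts only events that start after the initial dose.

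**The concern.** The biopsy is an invasive procedure done for the study's biomarker analysis, in patients who have consented but have not been treated. The recording window opens only afterwards. If a patient bleeds or develops an infection from the biopsy before dosing, the written rules do not make that an AE. They therefore do not make it an SAE either, and they do not start the 24-hour report to the sponsor.

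A patient harmed by the biopsy and for that reason never dosed is the worst case, because nothing about that patient reaches the database. There is no independent data monitoring committee; Protocol Section 11 relies on the sponsor's review of emerging safety data, and that review depends on events being reported.

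A second, smaller issue lies in the SAP. Section 7.2 asks whether an event that began before dosing became worse afterwards, but the protocol requires no AE record from before dosing to compare with.

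**Working it through.** No sample size, power or error rate is involved, so the check sets the rules side by side.

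1. **Can a pre-dose biopsy complication be an AE or SAE?** The AE definition requires that the patient has been given study treatment, and Section 10.2.5.2 defines an SAE as an AE with a serious outcome. The SAE inherits the limit. The 24-hour rule in Section 10.2.5.3 applies whatever the cause, but only to an SAE, so it does not clearly reach an event before dosing.

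2. **Does another rule reach it?** Section 10.2.5.3 extends SAE reporting in one direction only: after the window closes, and only where study treatment is the suspected cause. The rapid-notification list in Section 10.2.5.4 has no item for study procedures. No visible rule covers the time from consent to first dose.

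3. **What else would show it in a treated patient?** Medical history is updated on Day 1 before dosing (Table 1, note 5), with no grade specified. Medications from the 28 days before Day 1 are recorded (note 21), which covers the Day -28 to Day -1 window. A complication that starts after first dose is recordable as an AE. The first two routes specify neither grade nor seriousness and start no expedited report.

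4. **What else would show it in a screen failure?** Only the site's source records and its screening log. Nothing enters the database.

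5. **Do the SAP's two definitions agree?** They do not. Take an event that begins before dosing and worsens afterwards: Section 7.2 counts it and the Definitions table does not. An event on Day 1 shortly before the infusion is also counted by Section 7.2, which works by date, but not by the Definitions table.

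6. **Is there a pre-dose grade for the worsening comparison?** Select laboratory parameters have baseline CTCAE grades (SAP Section 7.7). Residual toxicity from earlier therapy must, with listed exceptions, be grade 1 or less or back to baseline at entry (Protocol Section 7.2.2.1). For other events, including a biopsy bleed or infection, no pre-dose grade is specified.

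7. **Do the date rules preserve a pre-dose onset?** Not when the date is incomplete. Under SAP Section 4.8.1 a completely missing onset date is set to the date of first dose, and so is a partial date from an earlier month or year. A pre-dose onset recorded that way becomes a first-dose onset. Section 7.2 also treats a missing attribution as related to study drug.

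**The case against.** The strongest reply is that starting at first dose is a deliberate and consistent choice. The AE definition, Section 10.2.5.3, Table 1 and SAP Exhibit 4 agree with one another, and the safety objective concerns CDX-3379 with cetuximab, not the biopsy. The biopsy is limited to sites of acceptable risk, archival tissue is possible, and efficacy conclusions do not depend on any of this. All of that stands. It shows that the window is coherent for drug safety; it does not supply a rule for harm from a procedure that the study itself requires.

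Three stronger readings are tempting, and the documents do not support them.

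- A reader might infer that biopsy harm is never captured or that nobody would know of it. The Day 1 history update, the medication look-back and the site's own records contradict this for treated patients, and the site would hold source records even for a screen failure. One bullet among the AE clarifications in Section 10.2.5.1 is redacted, Section 8 is not visible, and biopsy details are left to a laboratory manual, so an absolute statement is not possible.
- A reader might try to put a number on unrecorded serious events. The documents state neither how many patients have a fresh biopsy nor how often serious complications follow, so any such count would rest on assumed rates alone.
- A reader might infer that a persisting complication must be blamed on study treatment, or that treatment-emergent counts are badly wrong. Investigators judge causality event by event, and the unrelated category allows for other explanations. Worsening after first dose falls inside the window and can be recorded as an AE, so few treatment-emergent events should be lost. The effect on those counts is probably small.

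**Conclusion.** The gap is real and is one of participant protection. Between consent and first dose the visible text has no rule for reporting serious procedure-related events, although the default core biopsy falls in that period. It concerns every patient who has a fresh biopsy: among the approximately 45 planned patients, those not using approved archival tissue, plus any biopsied screen failures. How many of these would have a complication is unknown. The response rate, its confidence interval and the other efficacy results are untouched.

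The conflict between the SAP's two treatment-emergent definitions is a clear defect of limited numerical effect. It would need correcting even if the recording window stayed as it is.

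The conclusion assumes that neither the redacted AE bullet nor Section 8 contains a reporting rule for procedures before dosing. If either does, the point reduces to aligning Section 10.2.5.3 and Table 1 with it and settling the SAP definition.

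**What to change.** **Protocol.** In Section 10.2.5.3 and the AE row of Table 1, require that from signed consent to first dose the site records and reports all SAEs, and any AE related to a protocol-required procedure, with onset date and grade. State that this includes patients who fail screening after the biopsy, and adjust the AE definition and the screen-failure sentence in Section 10.1.1 to allow it. Keep the present rule for all AEs from first dose.

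**SAP.** List the pre-dose procedure-related events separately from treatment-emergent events. Use one treatment-emergent definition in the Definitions table and Section 7.2. If the worsening limb is kept, name the pre-dose record that supplies the grade: the protocol change above would not provide one for ordinary pre-existing conditions, so these would need, for example, a CTCAE grade on the Day 1 medical history. Section 4.8.1 should not move an onset known to be before dosing to the date of first dose.

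**Cost.** The existing AE and SAE forms would be used earlier, with a few more records and no new procedure. The downside is minor site work and a listing that includes some untreated patients. The protocol change reaches only patients screened after it takes effect, and stage 1 was already complete at Amendment 1. The SAP correction does not depend on enrollment.
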